5.4 Patient Withdrawal and Replacement

A patient is free to withdraw from the study at any time. A patient may be withdrawn for any of the following reasons:

- a. Disease progression (PD)
- b. AEs
- c. Major protocol violation
- d. Patient withdrew consent for study treatment either during the Core Phase or during the Extension Phase
 - Patients may voluntarily withdraw consent from study treatment at any time
- e. Investigator's discretion
- f. Start of new anticancer therapy

If a patient is withdrawn from dosing, the Sponsor will be notified and the date and reason(s) for the withdrawal will be documented in the patient's eCRF. If a patient is withdrawn, efforts will be made to perform all discharge assessments, if possible ([Appendix 1](#)). Other procedures may be performed at the principal investigator's (PI's) (or designee's) and/or sponsor's discretion. If the patient is in-house, these procedures should be performed before the patient is discharged from the clinic. The PI (or designee) may also request that the patient returns for an additional

Follow-up Visit. All withdrawn patients will be followed until resolution of all their AEs or until the unresolved AEs are judged by the PI (or designee) to have stabilized.

Patients who withdraw during the Core Phase may be replaced following discussion between the PI and sponsor.

5.5 Study Termination

The sponsor has the right to terminate this study at any time. Reasons for terminating the study early may include, but are not limited to, the following:

- The incidence or severity of AEs in this or other studies indicates a potential health hazard to patients
- Overall patient enrollment is unsatisfactory
- Poor protocol adherence
- Inaccurate or incomplete data recording
- Good Clinical Practice (GCP) noncompliance
- Study activity is completed (ie, the last patient accrued in the Extension Phase has been discontinued from the study due to intolerable toxicity, disease progression or voluntary withdrawal)

The sponsor will notify the PI if a decision is made to terminate the study. Should this be necessary, prematurely discontinued patients should be seen as soon as possible for an EOT Visit and Safety Follow-up Visit (Core and Extension Phase).

The PI may be informed of additional procedures to be followed in order to ensure that adequate consideration is given to the protection of the patient's interests. The PI will be responsible for informing the EC of the early termination of the study.

5.6 Data Entry in the eCRF

Data collection on the eCRF must follow the instructions described in the eCRF completion guidelines.

6 STUDY TREATMENTS

6.1 Description, Storage, Packaging, and Labeling

Pamiparib is provided in 20-mg or 60-mg capsules, based upon availability and approval status. Pamiparib capsules will be provided in 30- [REDACTED].

Itraconazole will be provided as 100 mg capsules in 60-count packs.

Rifampin will be provided as 300 mg capsules in 60-count packs.

Excipients contained in the pamiparib capsule are listed in the [Investigator's Brochure](#). Excipients contained in the rifampin and itraconazole capsules are listed in their respective product inserts.

The contents of the labels will be in accordance with all applicable local regulatory requirements. Labels will include at a minimum: drug name, dose strength, contents, sponsor, protocol number, bottle number, directions for use, storage conditions, caution statements, retest or expiration date, and space to enter the patient number and name of investigator

6.1.1 Handling and Storage

The instructions for drug ordering are in the pharmacy binder. Pamiparib will be dispatched to a study center only after receipt of the required documents in accordance with applicable regulatory requirements and the sponsor's procedures. The investigator or pharmacist/designated personnel are responsible for maintaining the drug supply inventory and acknowledging receipt of all pamiparib shipments. Pamiparib must be stored in a secure area with access limited to the investigator and authorized study center personnel and under physical conditions that are consistent with pamiparib specific requirements.

Pamiparib must be kept at the condition as specified on the labels. [REDACTED].

Itraconazole should be stored below 25°C and rifampin should be stored below 30°C.

6.2 Study Treatment Administration

Core Phase

All doses should be administered in the morning.

On the days of PK sampling (Days 1 and 10 in Part A and Days 1 and 7 in Part B), patients are required to fast for at least 8 hours before and 4 hours after study drug administration. Water is allowed during the fasting period, except 1h predose and 1h postdose. Rifampin (Part A) or itraconazole (Part B) will be administered first, followed within 5 minutes by pamiparib. Both study drugs should be taken with approximately 240 mL of water.

Patients enrolled in Part A will receive rifampin once a day on Day 3 to 9 and on Day 11 in the fasted state (at least 2 hours predose) and will continue to fast for 1h postdose. Water is allowed during the fasting period.

Patients enrolled in Part B will receive itraconazole once a day on Days 3 to 6 and on Day 8 approximately 30 minutes after completing a meal.

Extension Phase

During the Extension Phase, pamiparib capsules will be administered orally at 60 mg, twice a day 10 to 12 hours apart on Days 1 to 28 of a 28-day cycle.

6.3 Randomization

This is a nonrandomized study. The study has a fixed treatment sequence.

6.4 Blinding

This is an open-label study.

6.5 Study Treatment Compliance

During the Core Phase of the study, the following measures will be employed to ensure treatment compliance:

- All doses will be administered under the supervision of suitably qualified study site staff.
- Immediately after dose administration, visual inspection of the mouth and hands will be performed for each patient.
- At each dosing occasion, a predose and postdose inventory of pamiparib (Parts A and B), rifampin (Part A) and itraconazole (Part B) will be performed.

6.6 Drug Accountability

The investigator (or designee) will maintain an accurate record of the receipt of pamiparib capsules received, including the date in which they were received. One copy of this receipt will be returned to the Sponsor when the contents of the shipment have been verified. In addition, an accurate drug disposition record will be kept, specifying the amount dispensed to each subject; subject identification number; date of dispensing; and lot number(s) pamiparib, rifampin, and itraconazole. This drug accountability record will be available for inspection at any time. At the completion of the study, the original drug accountability record will be available for review by the Sponsor upon request.

For each batch of unit doses, the empty used unit dose containers will be discarded upon satisfactory completion of the compliance and accountability procedures. Any unused assembled unit doses will be retained until completion of the study. A record of quantities destroyed or returned to BeiGene shall also be documented.

At the completion of the study, all unused pamiparib capsules will be returned to the Sponsor or disposed of by the study site, per the Sponsor's written instructions.

Rifampin and itraconazole will also be subject to accountability procedures, and the CRU staff will not destroy unused supplies of rifampin and itraconazole until drug accountability and reconciliation has been performed by the Study Monitor.

6.7 Dose Holds and Modifications

AEs should be assessed as best as possible regarding their relatedness to study drug. Investigators should make every effort to maintain dose intensity in patients.

Core Phase

Patients who experience AEs that require dose holds should be discontinued from the Core Phase. Patients who experience AEs deemed related to rifampin or itraconazole are eligible to enter the Extension Phase.

Extension Phase

Dosing of pamiparib can be withheld for up to 28 days consecutively (up to 56 days consecutively for investigational drug-related anemia). If drug is planned to be held > 28 days (> 56 days for investigational drug-related anemia), the medical monitor should be contacted before permanent patient discontinuation from the study drug.

Criteria for treatment modifications and suggested guidelines for the management of some toxicities related to pamiparib are summarized below. These general guidelines may be modified at the discretion of the investigator based on discussions with the medical monitor and the best clinical judgment at that time; any decisions should be documented. Any toxicities related to pamiparib or placebo should be managed according to standard medical practice.

A maximum of 2 dose reductions is allowed before the patient must be permanently withdrawn from study drug. Dose levels for pamiparib are summarized in [Table 1](#). Pamiparib will be dose modified as outlined in [Table 2](#).

Table 1: Dose Levels for Pamiparib

Dose Level	Pamiparib
1	60 mg PO BID
-1	40 mg PO BID
-2	20 mg PO BID

Abbreviations: PO = oral; BID = twice daily.

Pamiparib may be dose-reduced for a maximum of 2 dose reductions.

Table 2: Criteria for Modification of Pamiparib Dosing for Related Adverse Events

Toxicity		Recommended Dose Modification ^a
Hematologic		
Anemia (hemoglobin, Hgb)		
Hgb < 9.0 g/dL		
 • First occurrence of Hgb < 9.0 g/dL: Hold pamiparib and treat as medically indicated to get Hgb to ≥ 9 g/dL, and then ↓ pamiparib by 1 dose level to 40 mg BID
Grade 2 (Hgb < 10-8 g/dL)	Hgb < 10-9 g/dL	
 • Continue dosing at current dose level and treat with appropriate supportive care as medically indicated
	Hgb < 9-8 g/dL	
 • Subsequent occurrence following dose reduction for anemia: 
 ○ Continue pamiparib without interruption with appropriate supportive care based on clinical assessment OR ○ Hold pamiparib and treat as medically indicated to get Hgb to ≥ 9 g/dL, then restart at reduced dose level OR ○ Hold pamiparib and treat as medically indicated to get Hgb to ≥ 9 g/dL, then ↓ pamiparib by 1 additional dose level to 20 mg BID
Grade 3 (Hgb < 8 g/dL)		
 • Subsequent occurrence following dose reduction for anemia: 
 ○ Continue pamiparib without interruption with appropriate supportive care based on clinical assessment OR ○ Hold pamiparib and treat as medically indicated to get Hgb to ≥ 9 g/dL, then restart at reduced dose level OR ○ Hold pamiparib and treat as medically indicated to get Hgb to ≥ 9 g/dL, then ↓ pamiparib by 1 additional dose level to 20 mg BID
Grade 4 (life-threatening consequences; urgent intervention indicated)		
 • Second occurrence following dose reduction for anemia: 
 ○ Hold pamiparib and treat as medically indicated to get Hgb to ≥ 9 g/dL, then ↓ pamiparib by 1 additional dose level to 20 mg BID • Third occurrence following 2 dose reductions for anemia: 
 ○ Discontinue pamiparib if anemia is not caused by any other confounding event, eg, GI hemorrhage. ○ Hold pamiparib and treat as medically indicated to get Hgb to ≥ 9 g/dL, then restart at reduced dose level.

Toxicity	Recommended Dose Modification ^a

Note:
 
 Weekly hematology test should be done for the first 3 cycles during the study. For all Grade 2 or higher anemia, hematology test should be done weekly thereafter until adequate recovery. For any patients showing Hgb dropping > 2 g/dL especially within a short time without alternative explanation such as gastrointestinal bleeding, ↓ pamiparib by 1 dose level should be considered. Dose increase can be considered in certain cases, depending on approval from the medical monitor, provided Hgb has been maintained above 9 g/dL for at least 3 months. 	

Neutropenia (ANC)
	

Grade 3 (ANC < 1.0 - 0.5 × 10⁹/L)
	
Hold pamiparib until resolved to Grade ≤ 2 or baseline
 
 If resolved ≤ 7 days, then maintain dose levels If resolved > 7 days, then ↓ pamiparib by 1 dose level

Grade 4 (ANC < 0.5 × 10⁹/L)
	
Hold pamiparib until resolved to Grade ≤ 1 or baseline and ↓ pamiparib by 1 dose level

Febrile neutropenia (ANC < 1.0 × 10⁹/L with single temperature of > 38.3°C or sustained temperature of ≥ 38°C for > 1 hour)
	
Hold pamiparib until resolved and ↓ pamiparib by 1 dose level

Thrombocytopenia (PLT)
	

Grade 3 (PLT < 50 - 25 × 10⁹/L)
	
Hold pamiparib until resolved to Grade ≤ 1 or baseline and ↓ pamiparib by 1 dose level

Grade 4 (PLT < 25 × 10⁹/L)
	
Hold pamiparib until resolved to Grade ≤ 1 or baseline and ↓ pamiparib by 1 dose level

Renal
	

Estimated glomerular filtration rate (MDRD STUDY EQ; www.mdrd.com or Appendix 9)
	

If ≥ 60 mL/min/1.73 m² at baseline: < 30 to 15 mL/min/1.73 m² or If < 60 mL/min/1.73 m² at baseline: ≥ 50% reduction from baseline
	
Hold pamiparib until resolved to ≥ 60 mL/min/1.73 m²
 
 If resolved ≤ 7 days, then maintain dose levels If resolved > 7 days, then ↓ pamiparib by 1 dose level

Regardless of baseline: < 15 mL/min/1.73 m²
	
Permanently discontinue pamiparib

Hepatic
	

Bilirubin
	

Grade 2 (> 1.5 - 3.0 × ULN) Only applies to patients with normal bilirubin at baseline
	
Hold pamiparib until resolved to Grade ≤ 1 or baseline
 
 If resolved ≤ 7 days, then maintain dose levels If resolved > 7 days, then ↓ pamiparib by 1 dose level

Toxicity	Recommended Dose Modification ^a
Grade 3 (> 3.0 - 10.0 × ULN)	Hold pamiparib until resolved to Grade ≤ 1 or baseline 
 If resolved ≤ 7 days, then maintain dose levels If resolved > 7 days, then ↓ pamiparib by 1 dose level
Grade 4 (> 10.0 × ULN)	Permanently discontinue pamiparib Note: If Grade 3 or 4 hyperbilirubinemia is due to the indirect (unconjugated) component only, and hemolysis as the etiology has been ruled out as per institutional guidelines (eg, review of peripheral blood smear and haptoglobin determination), then ↓ pamiparib by 1 dose level and continue treatment at the discretion of the investigator in discussion with the medical monitor
Aspartate aminotransferase (AST) and/or alanine aminotransferase (ALT)	
Grade 3 (> 5 and ≤ 20 × ULN)	Hold pamiparib until AST and/or ALT resolved to ≤ 5 × ULN or baseline 
 If not resolved within 7 days to ≤ 5 × ULN*, then pamiparib should be decreased by 1 dose level If second episode, permanently discontinue pamiparib *if other etiologies have been reasonably excluded and not solely based on abnormality/increase of AST/ALT laboratory results
Grade 4 (> 20 × ULN)	Permanently discontinue pamiparib
Pancreatic	
Pancreatitis	
Grade 3 or 4	Permanently discontinue pamiparib
Cardiac	
Cardiac - Prolonged QTc interval	
QTcF > 500 msec or Change in QTc interval > 60 msec from the highest value at baseline or predose	
 Obtain triplicate electrocardiograms (2 to 3 minutes apart) ~1 hour after initial electrocardiogram If mean QTcF > 500 ms or mean change in QTc interval > 60 msec, hold pamiparib until evaluation of electrocardiograms by cardiologist 
 Cardiology evaluation as soon as practical but within 7 days of initial abnormal electrocardiogram If mean QTcF > 500 ms or mean change in QTc interval > 60 msec is confirmed by cardiologist, permanently discontinue pamiparib
Cardiac – General	
Grade 3	Hold pamiparib until resolved to Grade ≤ 1 or baseline and ↓ pamiparib by 1 dose level 
 In the event of acute coronary syndrome, congestive heart failure and myocardial infarction, treatment should be permanently discontinued
Grade 4	Permanently discontinue pamiparib

Toxicity	Recommended Dose Modification ^a
Other AEs	
Grade 3	Hold pamiparib until resolved to Grade \leq 1 or baseline and ↓ pamiparib by 1 dose level No dose reduction required for asymptomatic laboratory abnormalities
Grade 4	Permanently discontinue pamiparib

Abbreviations: AE = adverse event; ALT = alanine aminotransferase; ANC = absolute neutrophil count; AST = aspartate aminotransferase; BID = twice daily; Hgb = hemoglobin; MDRD = Modification of Diet in Renal Disease; PLT = platelet (count); QTc = QT interval corrected for heart rate; QTcF = QT interval corrected for heart rate using Fridericia's formula; ULN = upper limit of normal.

- a. Dosing of pamiparib can be withheld for up to 28 days consecutively (up to 56 days consecutively for investigational drug-related anemia).

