5 STUDY POPULATION

5.1 Inclusion Criteria

Patients must meet all of the following criteria to be eligible for the study:

1. Voluntarily agreed to participate by signing an informed consent form (ICF)
2. Age \geq 18 years
3. Histologically or cytologically confirmed advanced or metastatic solid tumors that are refractory or resistant to standard therapy or for which no suitable effective standard therapy exists.
4. Disease that is evaluable per RECIST Version 1.1 or PCWG-3
5. ECOG performance status \leq 1 ([Appendix 2](#))
6. Life expectancy \geq 12 weeks
7. Ability to swallow whole capsules
8. Adequate hematologic and end-organ function, as defined by the following laboratory results (obtained \leq 14 days before day 1):
 - a. Absolute neutrophil count (ANC) \geq $1.5 \times 10^9/L$
 - b. Platelet count \geq $100 \times 10^9/L$
 - c. Hemoglobin \geq 9 g/dL (\geq 14 days after growth factor support or transfusion)
 - d. Estimated glomerular filtration rate \geq 50 mL/min/1.73 m² by the Modification of Diet in Renal Disease study equation (MDRD STUDY EQ; www.mdrd.com)
 - e. Total serum bilirubin \leq 1.5 x upper limit of normal (ULN)
 - \leq 4 x ULN, if Gilbert's syndrome or if indirect bilirubin concentrations suggestive of extrahepatic source of elevation
 - f. Aspartate and alanine aminotransferase (AST and ALT) \leq 3 x ULN or \leq 5 x ULN for patients with liver metastases
9. Females of childbearing potential and nonsterile males must use a highly effective method of birth control (see [Appendix 4](#)) while in the Core Phase of the study and for at least 6 months after the Core Phase is completed. In the Extension Phase, females of childbearing potential and nonsterile males must use a highly effective method of birth control (see [Appendix 4](#)) for the duration of the study and for at least 6 months after the last dose of study drug. Females of childbearing potential and non-sterile males must also

agree to not freeze/donate oocytes or sperm respectively.

10. Willingness and ability to comply with the protocol for the duration of the study

11. Body weight \geq 60 Kg at screening

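### The Table 2 renal restart target of 60 has no return-to-baseline option, so an Extension Phase patient who entered at eGFR 50-59 can recover fully and still not count as resolved

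*Protocol*

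**What the plan says.** Inclusion criterion 8d (Protocol 5.1) sets the renal entry floor at "Estimated glomerular filtration rate \geq 50 mL/min/1.73" m², calculated by MDRD. A baseline between 50 and 60 is therefore eligible.

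The renal row of Table 2 (Protocol 6.7) governs pamiparib holds for related adverse events in the Extension Phase. It has two triggers. With baseline of 60 or more, the hold starts when eGFR is below 30 (and not below 15). With baseline under 60, it starts at a fall of at least 50% from baseline. Both lead to one instruction: "Hold pamiparib until resolved to ≥ 60 mL/min/1.73" m². Resolution within 7 days keeps the dose; otherwise "If resolved > 7 days, then ↓ pamiparib by 1 dose level". The row identifies the equation as "MDRD STUDY EQ; www.mdrd.com or Appendix 9", and Appendix 9 gives both CKD-EPI and MDRD.

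Other rows accept return to baseline. Grade 3 neutropenia reads "Hold pamiparib until resolved to Grade ≤ 2 or baseline", and Grade 3 AST/ALT reads "Hold pamiparib until AST and/or ALT resolved to ≤ 5 × ULN or baseline".

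Two general limits apply: "Dosing of pamiparib can be withheld for up to 28 days consecutively" (longer only for drug-related anemia), and "A maximum of 2 dose reductions is allowed before the patient must be permanently withdrawn from study drug". Section 6.7 also lets the investigator depart from these guidelines after discussion with the medical monitor, provided the decision is documented.

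**The concern.** The row measures the injury against the patient's own baseline but measures recovery against a fixed value that some eligible patients did not have at entry. Renal function that has returned to where it started is not counted as resolved.

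For such a patient the 7-day branch that keeps the dose is closed. If eGFR later reaches 60, the restart is one level down, which uses one of the two permitted reductions. If it does not, the hold runs toward 28 days, and the medical monitor must be contacted before permanent discontinuation. At stake is pamiparib dosing for a patient whose kidneys have recovered, in a section that asks investigators to maintain dose intensity.

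**Working it through.** **1. Rows that accept return to baseline.** Neutropenia Grades 3 and 4, thrombocytopenia Grades 3 and 4, bilirubin Grades 2 and 3, AST/ALT Grade 3, cardiac general Grade 3, other AEs Grade 3: nine rows. The anemia rows lack the option, but their target (hemoglobin 9 g/dL) equals the entry minimum (9 g/dL), so nothing conflicts. Febrile neutropenia has no numeric target. The QTc row mentions baseline only to define its trigger. In the renal row, the restart value (60) is above the entry floor (50).

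**2. Same equation at baseline and recovery.** Trigger = 0.5 × baseline. Required recovery = 60 / baseline. Because eGFR varies as creatinine to the power -1.154 (MDRD) or, in this range, -1.209 (CKD-EPI), required creatinine relative to baseline = (60 / baseline)^(-1/1.154) or (60 / baseline)^(-1/1.209).

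| Baseline eGFR | Hold at or below | Full recovery reaches 60? | eGFR needed, relative to baseline | Creatinine needed, MDRD | Creatinine needed, CKD-EPI |
|---|---|---|---|---|---|
| 50 | 25.0 | No | 60/50 = 1.20 | 0.854 | 0.860 |
| 55 | 27.5 | No | 60/55 = 1.09 | 0.927 | 0.931 |
| 59 | 29.5 | No | 60/59 = 1.02 | 0.986 | 0.986 |

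At a baseline of 60 or more, return to baseline meets the target.

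**3. Baseline by MDRD, recovery by CKD-EPI.** Using the Appendix 9 equations without the race factor, and with ages chosen for illustration, solve CKD-EPI = 60 for creatinine and evaluate MDRD at that creatinine. Below the resulting MDRD baseline, a patient whose creatinine returns exactly to its baseline value still has CKD-EPI under 60.

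| Patient | MDRD baseline below which full recovery fails | CKD-EPI at the creatinine giving MDRD 55 |
|---|---|---|
| Woman, 40 | 52.7 | 62.7 (passes) |
| Man, 40 | 54.1 | 61.1 (passes) |
| Woman, 60 | 55.5 | 59.4 (fails) |
| Man, 60 | 56.9 | 57.9 (fails) |
| Man, 70 | 59.0 | 55.7 (fails) |
| Man, 75 | 60.2, so the whole stratum | 54.6 (fails) |

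**4. Cost of missing the 7-day window.** One level is 60 to 40 mg BID: (60 - 40)/60 = 33% less.

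**5. Reach.** The documents give no usable renal event rate; the protocol's summary of the first-in-human study lists only the most frequent Grade 3 related events. Both rates here are assumptions: 10-30% of about 24 patients have baseline 50-59, and 1-10% of those meet the trigger. Then 24 × 0.10 × 0.01 = 0.02 and 24 × 0.30 × 0.10 = 0.72 patients. This counts all 24 patients and ignores relatedness. Table 2 covers only pamiparib-related events and the Extension Phase is optional, so the true figure should be lower.

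**The case against.** The strongest objection is that Table 2 does not require one equation. Criterion 8d fixes entry on MDRD, while Table 2 also allows Appendix 9, which recommends CKD-EPI, and advises against MDRD, when values above 60 are wanted. A target of 60 could therefore point to CKD-EPI at recovery, and step 3 shows that this releases part of the stratum. That stands as a limit. A reader might infer that same-equation use is the expected case, because Appendix 9 also ties CKD-EPI to creatinine in mg/dL and MDRD to µmol/L. The appendix supports both readings and does not decide between them. On either reading some fully recovered patients fail, and restart should not depend on a change of formula.

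Second, section 6.7 presents the table as guidance that can be modified with the medical monitor, and a fully recovered patient is an obvious case for using that discretion. This softens the effect considerably. It does not make the rule right, since the row names this stratum and then needs an exception for its recovered members.

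Third, a stricter renal target could have been intended as caution after a fall of at least half in eGFR. The documents give no such rationale.

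**Conclusion.** The renal restart rule is wrong as written for baseline eGFR of 50 up to just under 60, and the matter is of minor severity. With one equation the failure covers the whole stratum. With MDRD at baseline and CKD-EPI at recovery it covers a part that depends on age and sex. Reach is probably well under one patient, on assumed rates.

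Two stronger readings are not supported. A reader might infer that every patient in this stratum is barred from restarting. The target is above their baseline but not out of reach, an equation switch may meet it, and the investigator can agree an exception with the medical monitor. A reader might also infer a threat to the study's results. A Core Phase patient who needs a hold leaves the Core Phase, so the renal row works only on Extension Phase dosing and the PK analysis is unaffected. The error also runs toward holding drug too long, not restarting too early.

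**What to change.** In the renal row of Table 2, add the words 'or baseline' after the 60 mL/min/1.73 m² target, matching the neighbouring rows. Patients with baseline of 60 or more are unaffected, because a return to baseline already means 60 or more for them.

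It would help to say in the same edit that baseline and recovery are compared by the same equation. Otherwise a man of 75 with MDRD baseline 55 reads 54.6 by CKD-EPI at unchanged creatinine and would narrowly miss his own baseline.

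The cost is two words in one table cell, plus a short clause if the equation is specified. It needs no extra data, visits or analysis and can wait for the next protocol amendment. Until then, the section 6.7 discretion, documented with the medical monitor, covers any case that arises.
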